### **Statistical Methods**

The cumulative proportion of participants hospitalized for the treatment of COVID-19 or dying during the first 28 days of the study will be estimated for each treatment group using the Kaplan-Meier method to take account of losses to follow-up and summarized graphically for each treatment group. The estimand is then the difference of the proportions in the 2 groups and its 95% CI will be presented as well as the associated Wald test. For the 95% CI, the corresponding estimate of the standard error is computed using Greenwood's formula. The Greenwood's formula to estimate the variance of the difference of proportions at Day 28 is [Var(SPF(28)) + Var(SPlacebo(28))]. Instead of dealing with S(ti) the log-log approach to CI will be used. The 95% CI will be computed for the estimate of L(t)= log(-log(S(t))), the log hazard function.

The above primary analysis will also be conducted for the planned interim analysis. Two-sided 95% CI (adjusted for the planned interim analysis) and associated p-value for the null hypothesis of no difference between treatment groups will be presented. Significance level will be determined using the O'Brien-Fleming approach at the interim analysis and the final analysis. The overall significance level is set at 5% (2 sided).

The estimate of required sample size is based on data from the BLAZE-1 Phase 2/3 trial among participants with mild to moderate COVID-19 who were at high risk for progressing to severe COVID-19 and/or hospitalization at enrollment. During the 29-day period following enrollment, the proportion of placebo-treated participants with a COVID-19-related hospitalization/emergency department visit was 7% in the Phase 3 portion of the trial.

[figure not shown]
This study is designed to have 90% statistical power to show a difference of 3.5% in the proportion of participants hospitalized/dying that did not receive COVID-19 therapeutic mAb between the treatment arms (PF-07321332/ritonavir versus placebo), using a 2-sided Type I error rate of 5%. Based on the above study, the proportion of hospitalization/death in the placebo arm is assumed to be 7%.

For a 2-sample proportion test, the sample size needed to detect this difference with 90% power at a 2-sided significance level of 5% was determined to be 1717 randomized participants.

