## 9.3.2. Primary Endpoint(s)/Estimand(s) Analysis

The primary efficacy analysis will be conducted using the mITT population.

The cumulative proportion of participants hospitalized for the treatment of COVID-19 or dying during the first 28 days of the study will be estimated for each treatment group using the Kaplan-Meier method to take account of losses to follow-up and summarized graphically for each treatment group. The estimand is then the difference of the proportions in the 2 groups and its 95% CI will be presented, as well as, the associated Wald Test. For the 95% CI, the corresponding estimate of the standard error is computed using Greenwood's formula. The Greenwood's formula to estimate the variance of the difference of proportions at Day 28 is [Var(SPF(28)) + Var(SPlacebo(28))]. Instead of dealing with S(ti) the log-log approach to CI will be used. The 95% CI will be computed for the estimate of  $L(t) = \log(-\log(S(t)))$ , the log hazard function.

The CI will be in the right range when transformed back to  $S(t) = \exp(-\exp(L(t)))$ . Antilogging this CI will give a 95% confidence interval for the difference itself.

The above primary analysis will be conducted for the planned interim analysis as well. Twosided 95% CI (adjusted for the planned interim analysis) and associated p-value for the null hypothesis of no difference between treatment groups will be presented. Significance level will be determined using the O'Brien-Fleming approach at the interim analysis and the final analysis. The overall significance level is set at 5% (2 sided).

For participants who complete Day 28 assessment (Day 34), they will be censored at their last visits. For participants who discontinue before Day 28 assessment or are lost to follow up, they will be censored at the last known date in the study.

The secondary analysis associated with primary endpoint will be conducted using the mITT2 population set.

Supplemental analyses will be performed to the primary efficacy endpoint:

- 1. An analysis in the mITT analysis set of the primary endpoint where participants that received a therapeutic COVID-19 mAb treatment post-baseline will be considered as an event for the endpoint (in addition to hospitalization for COVID-19 and death due to any cause) with mAb treatment date as the time of event.

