6. ANALYSES AND SUMMARIES

6.1. Primary Endpoint

6.1.1. Primary Endpoint/Estimand Analysis

6.1.1.1. Main Analysis

The primary endpoint is proportion of participants with COVID-19 related hospitalization or death from any cause through Day 28 in the mITT population. The cumulative proportion of participants hospitalized for the treatment of COVID-19 or death during the first 28 days of the study will be estimated for each treatment group using the Kaplan-Meier method to take account of losses to follow-up and summarized graphically for each treatment group.

The estimand is then the difference of the proportions in the 2 treatment groups and its 95% confidence interval will be presented, as well as, the associated two-sample proportion test. For the 95% CI, the corresponding estimate of the standard error is computed using Greenwood's formula (Kalbfleisch and Prentice; 1980). The Greenwood's formula to estimate the variance of the difference of proportions at Day 28 is $[Var(S_{PF}(28)) + Var(S_{Placebo}(28))]$. Instead of dealing with $S(t_i)$ we will use the log-log approach to CI. The 95% CI will be computed for the estimate of L(t) = log(-log(S(t))), the log hazard function.

$$Var(\hat{L}(t)) = Var[log(-log(\hat{S}(t)))]$$

The CI will be in right range when we transform back to $S(t) = \exp(-\exp(L(t)))$. Antilogging this confidence interval will give a 95% confidence interval for the difference itself.

The above primary analysis will be conducted for the planned interim analyses as well. Two-sided 95% CI (adjusted for the planned interim analyses) and associated p-value (two-sample proportion test) for the null hypothesis of no difference between treatment groups will be presented. Significance level will be determined using the O'Brien-Fleming approach at the interim analysis and the final analysis. The overall significance level is set at 5% (2 sided).

For participants who complete Day 28 efficacy assessment (Day 34 visit), they will be censored at their last visits. For participants who discontinue before Day 28 assessment or are lost to follow-up, they will be censored at the last known date in the study.

Participants will be analysed under the mAb stratum assigned at randomization/baseline.

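### The stated rule for the primary 95% CI does not produce an interval for the risk difference, and the protocol and SAP name the primary test differently

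*Protocol*

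**What the plan says.** Protocol 9.3.2 estimates the Day 28 risk of COVID-19-related hospitalization or death in each arm by Kaplan-Meier and takes the difference between arms as the effect. Of this difference it says "its 95% CI will be presented, as well as, the associated Wald Test". It then gives a variance for it: "The Greenwood's formula to estimate the variance of the difference of proportions at Day 28 is" the sum of the two arms' variances of S(28).

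The same paragraph then moves to another scale. Rather than work with S(t), a 95% CI is to be computed for L(t) = log(-log(S(t))). Two statements follow. The first is "The CI will be in the right range when transformed back to" S(t) = exp(-exp(L(t))). The second is "Antilogging this CI will give a 95% confidence interval for the difference itself".

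SAP 6.1.1.1 repeats the rule: "Antilogging this confidence interval will give a 95% confidence interval for the difference itself". It names a different test: "confidence interval will be presented, as well as, the associated two-sample proportion test". It uses that name again for the p-value and in neither place says which variance or which input proportions are meant. SAP Appendix 1 lists the primary model only as the Kaplan-Meier method.

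The synopsis (Protocol 1.1, Statistical Methods) agrees with 9.3.2 on the test ("its 95% CI will be presented as well as the associated Wald test") and says "the log-log approach to CI will be used", but has no antilog sentence. Protocol 9.3.3 and SAP 6.2.1 apply the primary method to the first key secondary endpoint in the mITT1 set.

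**The concern.** L(t) is a function of a single survival curve, so undoing it recovers that arm's survival and nothing about the contrast between arms. The antilog sentence nevertheless says the result is an interval for the contrast. Neither document contains a step that carries log-log limits to the risk-difference scale.

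The sentence governs the interval for the trial's main result, including the version adjusted for the interim look, and for the first key secondary endpoint. An analyst who follows it literally cannot report a risk-difference interval. One who sets it aside must choose a method the plan has not chosen.

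The test name adds a smaller uncertainty. The SAP's term could mean an unpooled test on the Kaplan-Meier estimates, which is the protocol's Wald test, or a pooled test on crude proportions, which ignores censoring.

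**Working it through.** **Inputs.** Placebo risk 7%, difference 3.5 points (so 3.5% on active), 90% power, two-sided 5%, N = 1717 and 5% dropout (Protocol 9.5); 1:1 allocation (Protocol 4.1); interim at 45%, with two-sided thresholds 0.002 and 0.049 (Protocol 9.4). N per arm = 1717/2, taken as 858. Assumption for the closed-form steps: no censoring, so Greenwood's variance equals the binomial variance.

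**The plan's own figure.** The pooled two-proportion formula gives 852 per arm, 1704 in total. Multiplying by the inflation for one Lan-DeMets O'Brien-Fleming look at 45% (1.0019) gives about 1707. The stated 1717 is within 1% of these, so the sample size is not in question.

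**A valid interval for the difference**
- Var(S_PF) = 0.035 × 0.965 / 858 = 0.00003936
- Var(S_Placebo) = 0.07 × 0.93 / 858 = 0.00007587
- SE = √(0.00003936 + 0.00007587) = 0.01073
- 95% CI = -0.035 ± 1.960 × 0.01073 = -5.60 to -1.40 points
- At the 0.049 level (z = 1.969): -5.61 to -1.39 points

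**What the log-log rule gives.** The delta-method SE of L is √Var(S) / (S × |log S|).
- Active: L = -3.335, SE 0.1825. Back-transformed risk 2.46% to 4.97%.
- Placebo: L = -2.623, SE 0.1291. Back-transformed risk 5.48% to 8.92%.

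These are arm-level intervals. The other literal readings fare no better:
- Difference in L = -0.711, SE = √(0.1825² + 0.1291²) = 0.2235, CI -1.150 to -0.273. Antilogged, this is 0.491 (0.317 to 0.761). It equals log(0.965)/log(0.930) = 0.0356/0.0726, a ratio of cumulative hazards.
- Applying exp(-exp(·)) to that interval gives 0.467 to 0.728, which has no meaning as a risk difference.
- log(-log(x)) requires 0 < x < 1, so it cannot be applied to a difference that may be zero or negative.
- Subtracting opposite arm limits gives -6.46 to -0.51 points, which is too wide.

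**A valid way to use the log-log limits.** Combining the arm limits by square-and-add (MOVER):
- lower = -0.035 - √((0.0350 - 0.0246)² + (0.0892 - 0.0700)²) = -5.69 points
- upper = -0.035 + √((0.0497 - 0.0350)² + (0.0700 - 0.0548)²) = -1.39 points

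This agrees with the Greenwood interval to about 0.1 point, but neither document describes it.

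**The test name.** With no censoring, unpooled Wald Z = -0.035/0.01073 = -3.260 (p = 0.0011). Pooled Z = -0.035/0.01077 = -3.250 (p = 0.0012).

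To allow for censoring, 40,000 trials per scenario were simulated with 5% dropout in each arm and event and dropout times uniform over 28 days (an assumption). The Kaplan-Meier Wald test was compared with a pooled test on crude proportions (an assumed reading of the SAP).

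| Scenario | Tests disagree | Rejection, Wald / crude | Coverage, RD ± z·SE / MOVER |
|---|---|---|---|
| 858 per arm, 3.5% vs 7%, threshold 0.049 | 0.51% (MC SE 0.04) | 90.0% / 89.9% | 95.0% / 95.3% |
| 386 per arm (45%), 3.5% vs 7%, threshold 0.002 | 0.64% (MC SE 0.04) | – | 94.9% / 95.5% |
| 858 per arm, 7% vs 7%, threshold 0.049 | – | 4.90% / 4.87% (MC SE 0.11) | – |

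Repeat runs gave 0.40% and 0.47% for the first disagreement figure and 0.69% for the second.

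**The case against.** The strongest reply is that the correct method is already on the page. The paragraph names the difference, gives its Greenwood variance and, in the protocol, attaches a Wald test. The difference ± z·SE follows at once. The log-log sentences mention only S and L, so they can be read as limits for each arm's curve, with only the closing sentence misplaced. Efficacy and futility decisions rest on p-value thresholds and not on this interval, and the valid intervals almost coincide.

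Most of this stands, and it limits the severity. It does not rescue the sentence. The text introduces the log-log step as a replacement for working with S(t) and ends by claiming an interval for the difference. An analyst must therefore disregard written instructions to reach the right answer, then choose between two valid methods.

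The synopsis can fairly be defended: it carries the Greenwood variance and the Wald test without the false claim, so it needs clarification and not correction. On the test, an unpooled Wald test on Kaplan-Meier proportions is a two-sample proportion test, and SAP Appendix 1's reliance on Kaplan-Meier to handle losses to follow-up argues against a crude pooled reading. The mismatch may therefore be wording only, but the SAP does not say so.

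**Conclusion.** The concern holds. The antilog sentence is mathematically wrong in Protocol 9.3.2 and SAP 6.1.1.1, and the mITT1 key secondary endpoint inherits it. Followed literally, it gives arm-level risks or a ratio near 0.49 where a difference of -3.5 points (-5.6 to -1.4) is wanted.

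The practical harm is a primary-interval rule that is incorrect and cannot be reproduced. No conclusion, sample size or alpha boundary changes, and either valid interval covers at about 95% with 5% dropout.

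The test-name mismatch is minor. Even on the least favourable reading, the two tests fall on opposite sides of the threshold in about 0.4% to 0.5% of trials at the final look and 0.6% to 0.7% at the interim.

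The figures rest on the planning rates, equal arms and, for the simulations, uniform event and dropout times. That the sentence is wrong rests on none of these. This should be fixed.

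**What to change.** - **Protocol 9.3.2 and SAP 6.1.1.1:** delete the antilog sentence and confine log-log intervals to the arm-specific Kaplan-Meier estimates. Clarify the same in the synopsis.
- **State one interval for the difference.** The simplest is RD = [1 - S_PF(28)] - [1 - S_Placebo(28)], SE = √(Var(S_PF(28)) + Var(S_Placebo(28))) with Greenwood variances, and CI = RD ± z·SE at the interim-adjusted level. A named and fully written combination of the arm-level log-log limits would also be valid.
- **Name one test.** Replace the SAP's term, in both places in 6.1.1.1, with the protocol's Wald test, RD/SE on the Kaplan-Meier estimates.
- **Record the date and reason.** Protocol Amendment 4 states that the interim objective was met, so the correction comes after the interim analysis and should be documented as such. If the efficacy boundary was crossed, the final analysis is supportive (Protocol 9.4, SAP 7.1); the documents do not say which boundary was met.

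The cost is text only. Protocol 9 requires major modifications of the primary analysis to appear in an amendment. Whether this counts as major is arguable, but the sentence is in the protocol, so the protocol text has to change in any case. Data, participants, sample size and alpha boundaries are untouched.

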### 9.3.3. Key Secondary Efficacy Endpoint(s)/Estimand(s) Analysis

# Proportion of participants with COVID-19 related hospitalization or death due to any cause through Day 28

The first key secondary efficacy endpoint is the proportion of participants with COVID-19 related hospitalization or death due to any cause through Day 28 in the mITT1 analysis set. The analysis for this endpoint is similar to the primary endpoint, but using the mITT1 analysis set.

# Time to sustained alleviation and time to sustained resolution of targeted COVID-19 sign/symptoms through Day 28

The key secondary endpoints of sustained alleviation and resolution will be defined for all targeted COVID-19 associated symptoms based on self-assessment.

Sustained alleviation of all targeted COVID-19 signs/symptoms is defined as the event occurring on the first of 4 consecutive days when all symptoms scored as moderate or severe at study entry are scored as mild or absent AND all symptoms scored mild or absent at study entry are scored as absent. The first day of the 4 consecutive-day period will be considered the First Event Date.

Sustained resolution is defined as when all targeted symptoms are scored as absent for 4 consecutive days. The first day of the 4 consecutive-day period will be considered the First Event Date.

For any symptoms not present at baseline, it must be absent at the last possible available day (prior to or at Day 25) to be counted as sustained alleviation/resolution. For symptoms with no reported severity in baseline, the symptom will have to be absent in order to consider alleviated/resolved (missing severity at baseline will be treated as mild).

Day 25 is the last possible day the symptom alleviation and resolution endpoints can be achieved (definition includes data from the subsequent three days) and Day 28 is the last day participants report their daily signs and symptoms.

The time to sustained symptom alleviation/resolution for the purpose of this study is defined as:

- For a participant with sustained symptom alleviation/resolution (event), time to event will be calculated as (First Event Date) (First Dose Date) +1.
- For a participant that either completes Day 28 of the study or discontinues from the study before Day 28 without sustained symptom alleviation/resolution (censored), censoring date will be at the last date on which symptom alleviation/resolution is assessed, and time will be calculated as (Censoring Date) (First Dose Date) +1 or day 25 whichever occurs first.

The decision to require 4 consecutive days with all targeted symptoms absent was based on exploratory analyses of data from the ACTIV-2/A5401 study, which suggested that this choice (rather than requiring fewer consecutive days) better captured sustained symptom resolution with low probability of subsequent relapse.

Participants who are hospitalized for the treatment of COVID-19 or die from any cause during the 28-day period will be classified as not achieving sustained symptom alleviation/resolution and will be censored at day 25.

Cox proportional hazard model analyses will be used for time to sustained symptom alleviation/resolution.

Time to sustained symptom alleviation/resolution will be summarized graphically using Kaplan-Meier plots for each of the treatment groups, the analyses will be done using mITT population, mITT1 population, and the mITT2 population.

### 9.3.4. Secondary Endpoint(s)/Estimand(s) Analyses

- Proportion of participants with severe signs/symptoms attributed to COVID-19 through Day 28
- Duration of each targeted COVID-19 sign/symptom
- Progression to a worsening status in 1 or more self-reported COVID-19 associated symptoms through Day 28
- Proportion of participants with a resting peripheral oxygen saturation ≥95% at Days 1 and 5.
- Proportion of participants with death (all cause) through Week 24

- PK of PF-07321332
- Viral titers (RT-PCR) measured in nasal swabs over time
- Number of COVID-19 related medical visits through Day 28.
- Number of days in hospital and ICU stay in participants with COVID-19 related hospitalization.

Details on the definitions and analyses of secondary endpoints will be described in the SAP.

### 9.3.6. Other Safety Analyses

Safety analyses will be carried out for the Safety population.

The safety assessments include AEs, laboratory assessments, physical examinations, and vital signs. No formal statistical analysis will be conducted on any of the other safety data listed above.

### 9.3.6.1. Laboratory

All clinical laboratory data will be subjected to clinical review, summarized by frequency of events and mean changes from baseline.

### 9.3.6.2. Physical Examination and Vital Signs

All physical examination and vitals will be descriptively summarized by treatment group.

Long-term COVID-19 symptoms will be collected by telephone interviews at Weeks 12 and 24 and PRO data (Global impression questions, EQ-5D-5L, WPAI) will be collected during the trial. These data are not planned to be included in the CSR.

## 9.3.7.1. PK Analyses

Descriptive statistics and graphical summaries of PF-07321332 concentrations will be generated. PK samples will be collected as described in the SoA. Additional PK sampling may be collected in a subset of participants via home health, site visit, or self-collected using Tasso, if feasible. Ritonavir concentrations may also be reported. PK data from this study may be combined with other studies and analyzed using population PK approaches. Results from any population PK analyses will be reported outside of the clinical study report.

PFIZER CONFIDENTIAL

Page 69

### 9.4. Interim Analyses

A planned interim analysis for efficacy and futility with a sample size-re-estimation will be conducted and reviewed by an independent E-DMC after approximately 45% overall participants have completed the Day 28 assessments in the mITT analysis set (ie, 28 days after randomization).

At the time of planning the Phase 2/3 study, there was uncertainty about the rate of COVID-19-related hospitalization or death in the primary analysis population, and about the treatment effect of PF-07321332. Hence, a sample size re-estimation will be conducted during the interim analysis based on conditional power. The sample size can be adjusted one time and the increase will be capped at 30%. A well-established method described by Cui, Hung, and Wang (1999) (implemented in EAST 6.5) will be used to control the Type I error probability.

The nominal significance level for the planned interim and final proportion of hospitalization/death analyses is determined by means of the Lan-DeMets procedure with an O'Brien-Fleming stopping boundary, with an overall 2-sided type I error rate of 5%.

For the interim analysis (45%), O'Brien-Fleming approach will be used for decision making, ie, reject H0 with 2-sided p-value  $\leq 0.002$ , or reject H1 with 2-sided p-value > 0.924. The final p-value for rejecting H0 will be  $\leq 0.049$  (2-sided) or reject H1 with 2-sided p-value > 0.049. The actual stopping boundaries will depend on the exact timing of the interim analysis. If the efficacy boundary is crossed at the interim analysis, a final analysis will be conducted as a supportive analysis.

Before any interim analysis is performed, the details of the objectives, decision criteria, dissemination plan, and method of maintaining the study blind as per Pfizer's SOPs will be documented and approved in an E-DMC Charter. In addition, the analysis details will be documented and approved in the SAP.

### 9.5. Sample Size Determination

The estimate of required sample size is based on data from the BLAZE-1 Phase 2/3 trial among participants with mild to moderate COVID-19 who were at high risk for progressing to severe COVID-19 and/or hospitalization at enrollment. During the 29-day period following enrollment, the proportion of placebo-treated participants with a COVID-19-related hospitalization/emergency department visit was 7% in the Phase 3 portion of the trial.

This study is designed to have 90% statistical power to show a difference of 3.5% in the proportion of participants hospitalized/dying that did not receive COVID-19 therapeutic mAb between the treatment arms (PF-07321332/ritonavir versus placebo) and were treated  $\leq 3$  days after COVID-19 symptom onset, using a 2-sided Type I error rate of 5%. Based on the above study, the proportion of hospitalization/death in the placebo arm is assumed to be 7%.

Using EAST (Version 6.5) for a 2-sample proportion test, the sample size needed to detect this difference with 90% power at a 2-sided significance level of 5% was determined to be 1717 randomized participants. Enrollment of participants that have received/expected to receive COVID-19 therapeutic mAb treatment is expected to be approximately 20% and will be limited to approximately 25% of participants. Enrollment of participants that had COVID-19 symptom onset >3 days prior to randomization is expected to be approximately 25% and will be limited to a total of approximately 1000 participants. Assuming a 5% dropout rate, the total sample size for this study will be approximately 3000 participants.

Study enrollment will be stopped after approximately 1717 participants are available for the primary analysis.

